## **Abstract**

**Background:** Periodontal destruction results mainly from the exacerbated host inflammatory response to the bacterial challenge. For this reason, research involving the modulation of host response has been developed aiming to facilitate the resolution of inflammation, as well as to promote tissue repair and periodontal stability. Recently, the use of omega-3 polyunsaturated fatty acids ( $\Omega$ -3 PUFA) and low-dose acetylsalicylic acid (ASA) was related to the production of enhanced lipidic mediators and to better clinical outcomes in the treatment of chronic periodontitis.

**Objective:** The aim of the present randomized controlled clinical trial was to evaluate the use of 900 mg  $\Omega$ -3PUFA and 100 mg ASA for 180 days as adjuvants to the non-surgical treatment (NST) of generalized aggressive periodontitis (GAgP).

**Methods:** Thirty-eight GAgP patients were submitted to subgingival debridement associated with  $\Omega$ -3 PUFA and ASA (n=19) or placebo (n=19).

**Results:** Both groups showed a statistically significant decrease ( $p<0.05$ ) in all clinical parameters, as well as a decrease in IL-1 $\beta$ , with no difference between treatments ( $p>0.05$ ). The TIMP-2 level significantly decreased in the control group and remained stable in the test group.

**Conclusion:** The proposed new therapy did not bring clinical benefits in the non-surgical treatment (NST) of GAgP.

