debridement session, when the patient received the pills. The professional responsible for patient recruitment ([name]), treatment ([name]), and the clinical measures ([name]) were distinct.

The sample size of the study was calculated based on the results obtained by a previous study that evaluated the effect of daily supplementation of  $\Omega$ -3 PUFA and low-dose ASA in the treatment of chronic periodontitis (El-Sharkawy et al., 2010). Considering  $\alpha = 5\%$  and  $\beta = 20\%$  (80% power) to detect an intergroup difference of at least 1.2 mm in the PD of pockets  $> 5$  mm, with a standard deviation of 0.8 mm, 16 patients would be needed in each group. To compensate possible attritions, 19 patients per group were included, obtaining a power  $> 80\%$ .

All diseased sites were instrumented in a single session by a trained operator ([name]). The patients received local anesthesia and one-stage full-mouth ultrasonic debridement (FMUD) (Wennström et al., 2005) by an ultrasonic device with specific tips for subgingival scaling. The patients were assigned to the following groups according to the randomization:

- Test Group (TG) (n=19): FMUD associated with 900 mg PUFA  $\Omega$ -3 + 100 mg ASA daily for 180 days;
- Control Group (CG) (n=19): FMUD and placebo.

All clinical measures were performed by one calibrated and blinded researcher ([name]). Clinical measures were performed at baseline, 3 and 6 months after the treatment, in all teeth, except third molars. The following clinical parameters were evaluated: 1) Probing depth (PD): distance from the bottom of sulcus/pocket to gingival margin; 2) Clinical attachment level (CAL): distance from the bottom of sulcus/pocket to cement–enamel junction (CEJ); 3) gingival recession (GR): distance from gingival margin to CEJ; 4) full-mouth plaque index (FMPI); and 5) full-mouth bleeding on probing (BoP). The clinical measures were assessed using a manual probe (North Carolina, Hu-Friedy). In addition, PD, CAL and GR measurements were done at six sites per tooth (mesiobuccal, buccal, disto-buccal, distolingual, lingual, and mesiolingual).

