## **Statistical Analysis Plan**

Mean and standard deviation were calculated for each parameter. The normal distribution was analyzed using the Shapiro-Wilk test. Demographic data were analyzed using the t-test for independent variables. The differences between the full-mouth variables were analyzed using a Generalized Estimated Equations Model and the reductions were evaluated by Generalized Linear Models, adjusted to baseline when indicated. The post-hoc test applied for each peer comparison was Bonferroni. The data were analyzed using the concepts of per-protocol and intention-to-treat. The statistical analysis was performed using significance level of 5%, using IBM SPSS.

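### IL-1β and TIMP-2 are reported in the abstract but not prespecified in these documents, and the TIMP-2 contrast sets two within-group results side by side with no between-arm comparison

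*Combined protocol and SAP*

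**What the plan says.** The results paragraph of the Abstract covers three things. The clinical parameters improved in both arms. So did one marker ("as well as a decrease in IL-1"β). For these the comparison of arms is given as "with no difference between treatments". TIMP-2 then has a sentence of its own: "The TIMP-2 level significantly decreased in the control group and remained stable in the test group". No between-arm estimate, interval or p-value goes with it.

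The Study Protocol introduces its list of measurements with "The following clinical parameters were evaluated". It names five: probing depth, attachment level, recession, plaque index and, as the last item, "5) full-mouth bleeding on probing (BoP"). The visit schedule is tied to the same kind of measurement: "Clinical measures were performed at baseline, 3 and 6 months after the treatment". No fluid or blood sample, sampled site, assay, unit or marker visit is described.

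The Statistical Analysis Plan names demographic data, full-mouth variables and reductions. Its repeated-measures sentence reads "The differences between the full-mouth variables were analyzed using a Generalized Estimated Equations Model". It applies Bonferroni to post-hoc pairwise comparisons and uses a 5% level. It names no marker.

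**The concern.** There are two linked problems.

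First, two results are reported for which the protocol and SAP give no definition or analysis. A reader cannot tell when the markers were measured, in what material, how many others were assayed, or whether they were secondary or exploratory. The Bonferroni step does not help, because it covers pairwise comparisons and not the number of outcomes.

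Second, the one sentence that suggests the combination did something biologically is a significant change in one arm set against no significant change in the other. That is not a comparison of the arms. Everything else in the results paragraph is reported as no different between treatments, so a reader looking for a biological signal will settle on TIMP-2, and the sentence as written cannot carry that reading.

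**Working it through.** **Step 1: where the markers appear.**

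| Item | Clinical parameters | IL-1β | TIMP-2 |
|---|---|---|---|
| Result in Abstract | yes | yes | yes |
| Between-arm statement in Abstract | yes, no difference | yes, no difference | none |
| Listed as a measurement in Study Protocol | yes (five) | no | no |
| Sampling, assay or visit described | yes | no | no |
| Named in SAP | full-mouth variables, yes | no | no |

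The plan has no figure of its own for either marker. Its only design calculation concerns probing depth, so there is nothing to reproduce and no stated power for a marker.

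**Step 2: what the TIMP-2 sentence can show.** I read the stable result in the test arm as a within-arm change that was not significant. Suppose the true TIMP-2 change is the same in both arms, and each arm's within-arm test is significant with probability p. The arms contain different patients, so the two tests are independent, and

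P(one significant, one not) = 2p(1 − p).

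- p = 0.05 (no change in either arm): 2 × 0.05 × 0.95 = 9.5%
- p = 0.3: 2 × 0.3 × 0.7 = 42%
- p = 0.5: 2 × 0.5 × 0.5 = 50%
- p = 0.7: 2 × 0.7 × 0.3 = 42%
- p = 0.8: 2 × 0.8 × 0.2 = 32%

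The particular direction reported (control significant, test not) has half of each probability, p(1 − p): for example 25% at p = 0.5 and 16% at p = 0.8. The documents do not give p, so this is a range and not an estimate. A discordant pair of within-arm results is common when the arms do not differ at all.

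**Step 3: number of tests, as illustration only.** With k independent null outcomes, each compared between arms once at 5%, the chance of at least one false positive is 1 − 0.95^k.

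- The two visible markers: 1 − 0.95² = 9.75%
- The five listed parameters: 1 − 0.95⁵ = 22.6%
- Five parameters plus two markers: 1 − 0.95⁷ = 30.2%

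These figures assume independence and a between-arm test of each outcome. The Abstract reports no such test for TIMP-2, so none of them is the error rate of the TIMP-2 sentence. They show only why the number of markers tested should be stated.

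**The case against.** The strongest reply is that silence in a short document is not evidence of an unplanned analysis. The protocol and SAP text is a brief past-tense summary bound with an abstract that already gives results. It refers to a registration record that is not available here. The list of five is expressly a list of clinical parameters in a paragraph about probing, so a laboratory marker would not be expected in it. The SAP's sentences on descriptive statistics and on reductions are not expressly confined to clinical measures.

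Most of this stands. A reader might infer that the markers were chosen after the results were seen. The documents do not support that: they show only that the markers are not described here. A reader might also suspect that TIMP-2 was picked from a large panel, and could compute 40.1% for ten markers or 64.2% for twenty from the same formula. Those panel sizes have no basis in the text. Two markers are visible, and one of them is reported as showing no difference between treatments. It is safer, too, to say that the SAP does not name the markers than that it excludes them.

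The reply does not remove the gap in sampling, timing and outcome status, which does not rest on the list of five. Nor does it touch the form of the TIMP-2 sentence, which would need a between-arm comparison even if the marker had been prespecified.

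**Conclusion.** The point holds in this form: neither marker is prespecified in these documents, and the only reported difference in pattern between arms rests on two separate within-group results. Under equal response in the arms, such a split arises with probability between 9.5% and 50% across the values of p tried. This assumes that stability means a non-significant change and that both arms have the same within-arm power.

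A reader might infer that the trial's conclusion is put in doubt. It is not. The Abstract's conclusion concerns clinical benefit, finds none, and draws nothing from TIMP-2. What changes is how much weight the TIMP-2 sentence can bear. The change is worth making because it is cheap and alters what a reader may properly take from the report.

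**What to change.** 1. Label IL-1β and TIMP-2 exploratory in the Abstract and report, unless a dated document that prespecified them can be cited. If it can, cite it and carry its definitions into the protocol and SAP.
2. List every marker assayed, with the sample type, sampled sites and sampling times, and state how many markers were tested.
3. Replace the TIMP-2 sentence with the baseline-adjusted difference between arms and its 95% confidence interval, and give the same for every marker. The SAP already uses generalized linear models with baseline adjustment for reductions, so no new method is needed.
4. A Holm or false-discovery-rate adjustment across markers is optional if they are labelled exploratory.

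The cost is one model per marker on data that the reported within-arm changes imply are already held, one table and a few words of labelling. The downside is a weaker TIMP-2 statement: the interval may well include no difference.

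### The Abstract concludes that there was no clinical benefit from p>0.05 in a superiority trial, and no between-group difference with a confidence interval is planned or reported

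*Combined protocol and SAP*

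**What the plan says.** The Study Protocol section describes a double-blind, placebo-controlled trial designed for superiority. It bases the sample size on PD, with "80% power) to detect an intergroup difference of at least 1.2 mm in the PD of pockets" deeper than 5 mm, and continues "with a standard deviation of 0.8 mm, 16 patients would be needed in each group". It then says "19 patients per group were included, obtaining a power" above 80%. Clinical measures are taken at baseline, 3 months and 6 months. They are PD, clinical attachment level (CAL), gingival recession (GR), full-mouth plaque index and full-mouth bleeding on probing (BoP).

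The Statistical Analysis Plan starts from arm-level summaries: "Mean and standard deviation were calculated for each parameter". Full-mouth variables are compared by generalized estimating equations (GEE), and reductions by generalized linear models (GLM) with baseline adjustment where indicated. On multiplicity it says "The post-hoc test applied for each peer comparison was Bonferroni", without giving the number of comparisons. On the error rate it says "The statistical analysis was performed using significance level of 5"%. It does not mention an estimated treatment difference, a confidence interval, or a margin below which a benefit would be considered negligible.

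The Abstract reports improvement in both arms "with no difference between treatments" (p>0.05). Its Conclusion is "The proposed new therapy did not bring clinical benefits in the non-surgical treatment (NST) of GAgP".

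**The concern.** Failing to reject the null hypothesis in a superiority trial means that superiority was not shown. It does not mean that benefit is absent. Moving from one to the other requires an interval estimate that shows which effects the data exclude, and that is what the plan and the Abstract lack.

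The conclusion is also broader than the design. Only PD in pockets >5 mm has a stated target difference and SD. The conclusion speaks of clinical benefit in general, after a results sentence that covers every clinical parameter. For CAL, GR, plaque and BoP the documents give no relevant difference and no power.

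A reader who takes the Abstract at its word would discard the combination as shown not to work, when the data may still be compatible with a moderate benefit.

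**Working it through.** **Inputs.** From the Study Protocol: difference 1.2 mm, SD 0.8 mm, 80% power, 16 per arm calculated and 19 per arm enrolled. From the SAP: significance level 5%. Assumptions: two-sided testing (sidedness is not stated), a two-sample t comparison and no baseline adjustment. No attrition rate is given, so 16 per arm serves as a lower case.

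**1. The plan's own figure.** The normal approximation is n = 2 × (SD/difference)² × (1.960 + 0.842)².
- With 0.8 and 1.2: 2 × 0.4444 × 7.849 = 6.98, so 7 per arm. An exact t calculation gives 9.
- The stated 16 is not reproduced. It appears when difference/SD = 1: 2 × 7.849 = 15.70, so 16 (17 by exact t).
- The documents do not show which input differs, so the 0.8 mm SD is not fully secure.
- Taking 0.8 mm at face value, power for 1.2 mm is 98.4% (16 per arm) or 99.4% (19 per arm).

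**2. What one unadjusted p>0.05 allows at SD 0.8 mm.** SE = 0.8 × √(2/n). The largest non-significant difference is t(0.975, 2n−2) × SE. The 95% upper limit at that point is twice as large.

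| Per arm | SE (mm) | t | Largest non-significant difference (mm) | 95% upper limit (mm) | Share of 1.2 mm |
|---|---|---|---|---|---|
| 19 | 0.2596 | 2.028 | 0.53 | 1.05 | 88% |
| 16 | 0.2828 | 2.042 | 0.58 | 1.16 | 96% |

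These are extreme cases, with p just above 0.05. In both, 1.2 mm lies outside the interval.

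**3. Power for smaller benefits.** With 19 per arm and SD 0.8 mm (noncentral t), power is 20% for 0.3 mm, 47% for 0.5 mm and 85% for 0.8 mm. A true 0.5 mm benefit would be missed slightly more often than it was found.

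**4. What is needed for the upper limit to pass 1.2 mm.**
- *Larger SD, unadjusted test.* Required SD = 1.2 / (2 × t × √(2/n)), which is 0.91 mm (19 per arm) or 0.83 mm (16 per arm). At SD 1.2 mm, one value that would give the stated n of 16, the limit could reach 1.58 or 1.73 mm.
- *Bonferroni over k comparisons at SD 0.8 mm.* The threshold is t(1 − 0.025/k) × SE, and the ordinary 95% half-width is then added. With 19 per arm, k = 3 gives 0.65 + 0.53 = 1.18 mm, and k = 4 gives 0.682 + 0.526 = 1.21 mm. With 16 per arm, k = 2 gives 0.667 + 0.578 = 1.25 mm.
- The Bonferroni figures combine an adjusted threshold with an unadjusted interval. For k = 4 and 19 per arm, that interval runs from 0.682 − 0.526 = 0.16 mm to 1.21 mm and so excludes zero.

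**The case against.** The best defence is power. With 98% to 99% power for 1.2 mm at the stated SD, a non-significant result on the powered endpoint does rule out the design difference. This stands for a single unadjusted test of PD in pockets >5 mm at SD 0.8 mm. It does not support a statement of no benefit of any size. The documents give 1.2 mm only as the difference to detect and nowhere say that smaller benefits are unimportant. The defence also does not carry over to the other parameters, or to the full-mouth variables that the SAP names.

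It can also be said that the GEE and GLM models already estimate group contrasts. That is correct. The gap is that reporting those contrasts with intervals is not specified. The Abstract does show its basis, because p>0.05 appears just before the conclusion, so this is an error of interpretation and reporting and does not invalidate the tests.

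A reader might go further and infer that the non-significant result is compatible with a benefit above 1.2 mm. The stated figures do not support that. It needs an SD above 0.8 mm, or Bonferroni-adjusted p-values over at least 4 comparisons with 19 per arm (2 with 16 per arm). The SAP does not state the number. Three same-visit comparisons between the groups with 19 per arm would stay at 1.18 mm, and a two-arm contrast in one reduction is a single comparison, which Bonferroni leaves unchanged.

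**Conclusion.** The point holds in a limited form. The conclusion goes further than the analysis supports, because it turns p>0.05 in a superiority trial into absence of benefit without an estimate or an interval.

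For PD in pockets >5 mm, at the stated SD and with one unadjusted two-sided test, 1.2 mm is excluded. Benefits up to about 1.05 mm (19 per arm) or 1.16 mm (16 per arm) may not be. These are ceilings for p just above 0.05. The actual estimate, SD and p-value are not given, so the real upper limit may be well below them, and baseline adjustment would narrow the interval. For the other clinical parameters, the documents do not allow any statement about which benefits are excluded.

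The documents do not show that the therapy works or that a 1.2 mm benefit was missed. They support only the statement that superiority was not shown.

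**What to change.** Add to the SAP, marked as added after results were known because the Abstract already reports them: *For PD of pockets >5 mm and for each other clinical parameter, the baseline-adjusted between-group difference from the GEE or GLM analysis will be reported with its two-sided 95% CI.* State the number of comparisons in each Bonferroni family, so that readers know which p-values are adjusted.

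Reword the Abstract's conclusion to say that *no statistically significant clinical benefit was shown*. Give the difference and CI, and describe the size of benefit that the upper limit excludes. Do not use 1.2 mm as a pass/fail margin for claiming no benefit, since it was set only as a difference to detect.

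The cost is small. The contrasts come from models already fitted, though the SAP does not name PD of pockets >5 mm, which may need its own fit. No new data are needed. The conclusion becomes less definite, but if the interval is narrow it gives a properly bounded negative result.

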## Study Protocol

This double-blind, placebo-controlled, randomized clinical trial was designed to evaluate the superiority of PUFA ω-3 + ASA vs. control. The study followed the CONSORT 2010 and the SPIRIT 2013 Statements. The trial was approved by the human subjects ethics board of Unesp (CAAE 66096817.3.0000.0077) and was conducted under the principles of the Helsinki Declaration of 1975, as revised in 2013. The study protocol was registered in ClinicalTrials.gov (NCT03093246).

Subjects with generalized grade C periodontitis were selected at the Division of Periodontics, Institute of Science and Technology, São Paulo State University (Unesp), Brazil. A complete dental exam was carried out and medical records were obtained. Subjects who fulfilled the inclusion criteria were invited to participate in the study. Each subject provided informed consent after a thorough explanation of the nature, risks, and benefits of the clinical investigations. The inclusion criteria were: 1) diagnosis of stages III/IV generalized grade C periodontitis (Papapanou et al, 2018); 2) presence of  $\geq 20$  teeth, excluding third molars and teeth indicated for extraction; 3) presence of  $\geq 6$  sites presenting PD  $\geq 5$  mm with bleeding on probing (BoP) and  $\geq 2$  sites with PD  $\geq 7$  mm (including incisors and first molars, in addition to three other non-contiguous teeth between them); 4) good general health; 5) at least 18 years old; and 6) agree to participate in the study and sign a written consent. Patients who 1) were pregnant or nursing; 2) were suffering from any other systemic disease (e.g., cardiovascular, diabetes, blood dyscrasias, immunodeficiency, etc.); 3) received antimicrobials or anti-inflammatory drugs in the previous 6 months; 4) received a course of periodontal treatment within the last 12 months; 5) smoked  $\geq 10$  cigarettes/day; 6) reported an allergy to ASA or seafood; 7) required antibiotic prophylaxis; 8) were currently using medication that could interfere with periodontal response; or 9) reported gastritis and/or gastric ulcers were excluded.

The randomization was done as follows: a researcher ([name]) generated a random computer sequence to determine the order in which the treatments would occur (test/control) according to the established sample. This sequence was kept in a brown/opaque envelope and was followed as the subgingival debridement were performed . The treatment was revealed only after the

debridement session, when the patient received the pills. The professional responsible for patient recruitment ([name]), treatment ([name]), and the clinical measures ([name]) were distinct.

The sample size of the study was calculated based on the results obtained by a previous study that evaluated the effect of daily supplementation of  $\Omega$ -3 PUFA and low-dose ASA in the treatment of chronic periodontitis (El-Sharkawy et al., 2010). Considering  $\alpha = 5\%$  and  $\beta = 20\%$  (80% power) to detect an intergroup difference of at least 1.2 mm in the PD of pockets  $> 5$  mm, with a standard deviation of 0.8 mm, 16 patients would be needed in each group. To compensate possible attritions, 19 patients per group were included, obtaining a power  $> 80\%$ .

All diseased sites were instrumented in a single session by a trained operator ([name]). The patients received local anesthesia and one-stage full-mouth ultrasonic debridement (FMUD) (Wennström et al., 2005) by an ultrasonic device with specific tips for subgingival scaling. The patients were assigned to the following groups according to the randomization:

- Test Group (TG) (n=19): FMUD associated with 900 mg PUFA  $\Omega$ -3 + 100 mg ASA daily for 180 days;
- Control Group (CG) (n=19): FMUD and placebo.

All clinical measures were performed by one calibrated and blinded researcher ([name]). Clinical measures were performed at baseline, 3 and 6 months after the treatment, in all teeth, except third molars. The following clinical parameters were evaluated: 1) Probing depth (PD): distance from the bottom of sulcus/pocket to gingival margin; 2) Clinical attachment level (CAL): distance from the bottom of sulcus/pocket to cement–enamel junction (CEJ); 3) gingival recession (GR): distance from gingival margin to CEJ; 4) full-mouth plaque index (FMPI); and 5) full-mouth bleeding on probing (BoP). The clinical measures were assessed using a manual probe (North Carolina, Hu-Friedy). In addition, PD, CAL and GR measurements were done at six sites per tooth (mesiobuccal, buccal, disto-buccal, distolingual, lingual, and mesiolingual).

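### The stated 16 per group does not follow from the printed inputs, which require 7 (normal approximation) or 9 (t-test) per group

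*Combined protocol and SAP*

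**What the plan says.** The sample size paragraph of the Study Protocol section gives the whole justification. The inputs come from earlier work in chronic periodontitis: "The sample size of the study was calculated based on the results obtained by a previous study". The targets are 5% alpha and 80% power "to detect an intergroup difference of at least 1.2 mm in the PD of pockets" deeper than 5 mm. The result follows directly: "with a standard deviation of 0.8 mm, 16 patients would be needed in each group". Only then is an allowance for losses added: "To compensate possible attritions, 19 patients per group were included, obtaining a power" above 80%.

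The paragraph does not name the test, say whether it is one-sided or two-sided, or say whether the SD belongs to a single visit or to a change from baseline. The Study Protocol section describes the trial as "designed to evaluate the superiority of PUFA ω-3 + ASA vs. control". The Statistical Analysis Plan sets the significance level at 5% and plans models both for the full-mouth variables and for their reductions.

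**The concern.** A difference of 1.2 mm against an SD of 0.8 mm is a standardised difference of 1.5, which is very large. Sixteen per group is about what a standardised difference near 1.0 would need, so the result looked too high for its inputs.

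The trial is complete, so what is at stake is reporting and interpretation. The Abstract reports no difference between treatments and concludes that there was no clinical benefit. How much such a result tells us depends on the difference the trial could detect, and a reader cannot establish that if the sample size does not follow from its own inputs.

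**Working it through.** **Inputs** (sample size paragraph): difference 1.2 mm, SD 0.8 mm, alpha 0.05, power 0.80, two equal groups. Two-sided testing is an assumption; one-sided testing is tried below. Standardised difference d = 1.2/0.8 = 1.5.

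**The plan's own figure.**
- Normal approximation: n per group = 2 × ((1.960 + 0.842)/1.5)² = 6.98, so **7**.
- Two-sample t-test (noncentral t): 8.06, so **9**.

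Neither gives 16.

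**Power on the printed inputs (two-sided t-test)**

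| n per group | Power |
|---|---|
| 8 | 79.7% |
| 9 | 84.8% |
| 16 | 98.4% |
| 19 | 99.4% |

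**Attrition.** The 16 is stated before the allowance. Going from 19 to 16 allows for 1 − 16/19 = 15.8% loss. Going from 19 to 9 would allow for 1 − 9/19 = 52.6%.

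**Other routes to 16.** Each rests on an assumption that the documents do not state.

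| Reading | n per group |
|---|---|
| One-sided 5% | 5.50 (6, normal); 6.30 (7, t-test) |
| Rank test, efficiency 0.955 or worst case 0.864 | 8.44 (9) or 9.33 (10) |
| 0.8 read as a variance | 8.72 (9, normal); 9.78 (10, t-test) |
| Bonferroni, alpha/3 or alpha/5 (t-test) | 10.85 (11) or 12.14 (13) |
| Change score, visits uncorrelated, SD = 0.8 × √2 = 1.13 mm | 13.95 (14, normal); 14.98 (15, t-test) |

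Two readings come close:
- **16 as a total.** The unrounded t-test figure is 2 × 8.06 = 16.1 in total, and 8 per group gives 79.7% power. Strict rounding up gives 18 in total.
- **0.8 mm as a single-visit SD**, with an unadjusted change score intended. This gives 14 or 15 per group.

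**What 16 per group would imply.** For 80% power by t-test, d must be about 1.02. That means a difference of about 0.82 mm at SD 0.8 mm, or an SD of about 1.17 mm at a difference of 1.2 mm. Neither is printed.

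**Detectable difference with 19 per group at 80% power.** d = 0.934. If SD 0.8 mm applies to the analysed outcome, this is 0.934 × 0.8 = 0.75 mm. With an SD of 1.17 mm it would be 0.934 × 1.17 = 1.09 mm.

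**The case against.** The best case for the plan is that the calculation is under-described rather than wrong. The Statistical Analysis Plan analyses reductions, so a change score is a natural outcome to size for. It also plans a normality check, so sizing for a rank test is conceivable. Combining a change score with uncorrelated visits (14.98) and the rank-test efficiency of 0.955 gives 14.98/0.955 = 15.68, which rounds up to 16 per group with 1.2 mm and 0.8 mm exactly as printed. Even under the change-score reading, t-test power is 82.7% at 16 and 88.9% at 19 per group, so the power claim survives. The other candidate, a total mislabelled as per group, sits badly with a paragraph that counts per group twice.

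Part of this stands. An arithmetic slip is not proved, and incomplete reporting may be the whole explanation. But the route to 16 stacks two assumptions that appear nowhere in the text. Mentioning reductions as an outcome does not make 0.8 mm a single-visit SD. The paragraph presents 16 as the result of the inputs it prints, and on those inputs it is not.

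It is also fair to say that the error is conservative and the trial is over. That limits the consequence but does not remove it, because the error is known to be harmless only if the printed inputs are the right ones, and the mismatch puts that in doubt.

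**Conclusion.** The concern holds. The printed inputs require 7 or 9 per group, and the stated 16 is nearly double the t-test figure. This assumes a two-sided comparison of two means; a one-sided test widens the gap. The number, its unit or an input is wrong or incompletely reported, and the documents cannot settle which. The mismatch itself is certain, while neither candidate explanation can be confirmed.

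The consequence is confined to reporting and interpretation. If the printed inputs are right, the trial was larger than its target required and the statement of power above 80% is true. The point should be corrected, but it casts no doubt on enrolment or on the analysis.

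**What to change.** Check the original calculation and the source study. Then state the test, the sidedness, whether 0.8 mm is the SD of a single visit or of a change, and whether 16 is per group or a total.

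- **If 1.2 mm and 0.8 mm are confirmed for the analysed outcome:** restate the requirement as 9 per group (t-test), with 98% power at 16 and 99% at 19 per group, and a detectable difference of about 0.75 mm at 80% power with 19 per group. Mark this as a correction, so that 9 is not read as the number originally planned.
- **If other inputs were used:** print them and recompute the sample size and power from them.
- **If the inputs cannot be recovered:** say so.

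Do not choose a difference or SD because it yields 16. The cost is a text correction after a check of the records, with no change to enrolment or analysis.
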